### **V. Data Analysis and Reporting**

#### **A. Statistical and Data Analysis:**

The primary statistical analyses for Aims 1-2 utilize paired, pre-, post- acute exercise measurements. As such, we will analyze the data using the two-sample, paired t-tests. This will contrast overall changes in

brain metabolism following acute exercise (i.e., pre- vs. post-exercise differences) and between the intensity groups (moderate vs. higher intensity). We will conduct residual analyses to assess the appropriateness of this methodology to evaluate assumptions of common variance, normally distributed errors, etc. In the event any of the measures do not conform to these foundational assumptions, the nonparametric analogs will be used instead, such as the Wilcoxon rank sum test of the within-subject pre- vs. post-exercise measures. These measures will follow the intent-to-treat principals. Though a randomized design, we will also construct exploratory analyses that incorporate other adjustments using ordinary least squares (OLS) regression on the change scores as the outcomes, also with residual analysis and modified approach if indicated. This will allow for model adjustment to further examine these relationships. One further relationship will involve combining the results of the AD and ND subjects in a single model as described in our Aims. We will use OLS in this context to test for interactions between AD and ND subjects with respect to the acute exercise response (moderate vs. higher intensity) for these pre-/post-exercise change score outcomes. Finally, we will model change score outcomes as functions of the various other change score measures. This approach will enable us to observe how changes in cerebral glucose metabolism are driven by acute-exercise influenced changes in circulating biomarkers. We will conduct similar residual analyses appropriate to the regression models utilized to ensure appropriate inferences are drawn. While descriptive and exploratory in nature, we anticipate that this approach will illuminate and/or confirm our pre-conceived metabolic processes that are related to the acute exercise response, and that it will help identify likely reasons for prior exercise trial successes and failures through mechanistic discovery. We believe this study fits perfectly within the study paradigm for PAR-18-877 by the NIA, which states that identifying precise cellular mechanisms will provide important therapeutic targets.

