Sample size justification. We powered our study based upon our primary variable of interest, cerebral glucose metabolism. Based on previous literature [6], the cerebral metabolic rate of glucose following acute exercise at (70% VO2max) ( $3.18 \pm 0.68$ ) was significantly lower compared with that of resting controls ( $4.25 \pm 0.27$ ). This study produced an effect size of 2.07 based on the independent t test design. However, given the small sample size of that initial study, we conservatively use much lower effect sizes. A two sample paired t test design with an effect size of 1.25 and a sample size of 15 AD subjects allocated to high intensity and 15 AD subjects allocated to moderate exercise would yield an estimated power of 91% using a conservative estimated effect size of 1.25. Dropping down to less than half the effect size produced in the preliminary data to 1.00 still provides 75% power, and using a still conservative 1.50 for the effect size indicates >95% power. (Power calculations were produced by nQuery Advisor® 7.0, 1995-2007.) We plan to recruit the same number of elderly healthy patients in the study. Accounting for a possible 10% attrition rate over the course of the study visits, we propose a total sample size of 60 (30 subjects in each diagnosis group with 15 individuals assigned to moderate and higher intensity acute exercise) Thus, we anticipate recruiting the sample size of 66, which will provide over 90% power based on a conservative estimate of the effect size from the literature and the use of paired difference scores for the primary endpoint, which should reduce variation in the response.

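### The randomised intensity contrast rests on unadjusted change scores whose variance reduction is asserted without a rest–exercise correlation; adjusting for the resting scan should be pre-specified.

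*Combined protocol and SAP*

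**What the plan says.** The first part of section V.A (Statistical and Data Analysis) makes t tests on within-person rest-to-exercise differences the primary analysis. These cover the overall change and the moderate-versus-higher contrast. Adjustment is secondary: the plan describes "exploratory analyses that incorporate other adjustments using ordinary least squares (OLS) regression on the change scores as the outcomes". The covariates are not named, and nothing says that the resting scan is one of them. A further OLS model tests the diagnosis-by-intensity interaction, again on change scores. The FDG-PET imaging text in section II.E allows paired t tests or linear mixed models for regional SUVR, also without naming a resting covariate.

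The sample size paragraph in V.A starts from a cited study with separate exercise and resting groups: mean 3.18 (SD 0.68) after exercise, 4.25 (SD 0.27) at rest. It says "This study produced an effect size of 2.07 based on the independent t test design". For 15 v 15 participants with AD, the planned design "would yield an estimated power of 91% using a conservative estimated effect size of 1.25". An effect size reduced "to 1.00 still provides 75% power", and "using a still conservative 1.50 for the effect size indicates >95% power". The paragraph closes by supporting its claim of over 90% power partly with "the use of paired difference scores for the primary endpoint, which should reduce variation in the response". Neither r nor an SD of the change is given.

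**The concern.** Differencing is one particular adjustment for the resting value, with the slope fixed at 1. Whether it lowers the variance depends on r and on the two SDs. The plan states the benefit as a general expectation, takes its effect size from an unpaired study, and does not carry it over to the change-score scale on which the test will be run. If r is modest, the stated power may not be met.

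The resting scan is collected from everyone. In a randomised contrast, regression on it lets the data set the slope. The residual variance is then never larger than that of the change score, apart from the small cost of estimating the slope. With about 15 people per arm within a diagnosis group, chance imbalance in resting metabolism is likely, and how it is handled affects the precision of the main comparison.

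**Working it through.** **Inputs.** From V.A: SD 0.68 (exercise), SD 0.27 (rest), mean difference 4.25 − 3.18 = 1.07, 15 per arm, planning effect sizes 1.00, 1.25 and 1.50. Assumed, because the documents do not state them: two-sided 5% alpha, the value of r, and (step 4 onwards) that 1.25 is expressed in units of the pooled SD.

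**1. The plan's own figures.** Pooled SD = √[(0.68² + 0.27²)/2] = √0.26765 = 0.517, and 1.07/0.517 = 2.07, as stated. An independent two-group t test (noncentral t, 28 df) gives 75.3%, 91.0% and 97.7% power at 1.00, 1.25 and 1.50. All three stated figures reproduce. A one-sample paired calculation with n = 15 would give 99.4% at 1.25, so the plan's 91% is a two-group figure.

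**2. Variance of a change score.** Var = 0.68² + 0.27² − 2r(0.68)(0.27) = 0.5353 − 0.3672r.

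**3. When is that a reduction?**
- Against the exercise scan alone, the natural comparator when both arms are exercise scans: 0.5353 − 0.3672r < 0.4624, so r > 0.27/(2 × 0.68) = 0.20. With equal SDs the threshold is 0.50.
- Against the pooled SD behind 2.07: 0.5353 − 0.3672r < 0.26765, so r > 0.26765/0.3672 = 0.73.

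**4. Power of the change-score test.** Raw difference held at 1.25 × 0.517 = 0.647, 15 v 15. The exercise scan alone (SD 0.68) would have 71% power.

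**5. Adjusted against change score.** The adjusted residual SD is 0.68√(1 − r²). Estimating the slope with 15 v 15 multiplies the variance by about 1 + 1/26 = 1.038. The last column is 1.038 × (adjusted SD/change SD)².

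| r | change SD | change-score power | adjusted SD | variance, adjusted ÷ change |
|---|---|---|---|---|
| 0 | 0.732 | 65% | 0.680 | 0.90 |
| 0.3 | 0.652 | 75% | 0.649 | 1.03 |
| 0.4 | 0.623 | 78% | 0.623 | 1.04 |
| 0.5 | 0.593 | 82% | 0.589 | 1.02 |
| 0.6 | 0.561 | 86% | 0.544 | 0.98 |
| 0.7 | 0.528 | 90% | 0.486 | 0.88 |
| 0.8 | 0.491 | 94% | 0.408 | 0.72 |
| 0.9 | 0.453 | 97% | 0.296 | 0.45 |

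The worst case is r = 0.27/0.68 = 0.40, where the true slope is exactly 1. There, power falls from 78.3% to 76.7%, a loss of under 2 points.

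**6. If the SDs are equal.** The ratio is 1.038 × (1 + r)/2, which is 0.68 at r = 0.3. Power for a difference of 1.25 SD then goes from about 80% to about 92%.

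**The case against.** A reader might infer from the 0.73 that differencing makes the intensity contrast noisier unless r is that high. The documents do not support this. Both arms of that contrast are exercise scans, so the analysis that ignores rest has SD 0.68, and on the quoted figures differencing already helps above about r = 0.20. The 0.73 applies only to the pooled SD from a rest-versus-exercise comparison.

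Four further points stand.
- The SDs are absolute metabolic rates from separate groups, while this trial's endpoint is cerebellum-referenced SUVR. No moderate-intensity SD is given. The plan never says that 1.25 is in units of 0.517.
- On the quoted SDs, adjustment gains nothing for r of about 0.2 to 0.5. The larger gains need r near 0, r of about 0.7 or more, or more nearly equal SDs.
- The figures are for 15 v 15. If the two diagnosis groups are pooled to about 30 v 30, change-score power on the same inputs is already 95% or more for r of at least 0.2, so adjustment adds little power.
- Rest and exercise visits are counterbalanced, so some resting scans follow the exercise bout. If that bout shifted a later resting scan, the change score would carry the shift with weight 1 and the adjusted estimate with weight b = r × 0.68/0.27. This weight exceeds 1 once r exceeds 0.40 (1.26 at r = 0.5). Carry-over is not shown to exist, but adjustment could enlarge it.

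It is also fair that the Aims define the outcome as change, and that OLS on change scores is already planned. Adding the resting value to that model gives the same intensity test as proposed here. What remains open is that the covariate is unnamed and the adjusted model is only exploratory.

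**Conclusion.** The point holds as one of pre-specification and unsupported justification. The plan does not name the resting scan as a covariate, and it claims a variance reduction without the correlation that decides it. If 1.25 is read on the 0.517 scale, with two-sided 5% alpha, change-score power is below the stated 91% until r reaches about 0.73; it is about 75% at r = 0.3 and 82% at r = 0.5.

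Adjustment is the better default because r is unknown and the trade is lopsided: at most about 4% more variance, against 12% less at r = 0.7, 55% less at r = 0.9, and about 32% less at r = 0.3 with equal SDs. It is not a guaranteed gain, and it does not show that the planned test is invalid or that the trial is underpowered. All sizes are illustrative, since the SDs are not on the SUVR scale.

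**What to change.** For the randomised intensity contrast only, pre-specify as primary a regression of the exercise-visit value (or, equivalently, the change) on intensity, resting-visit value and visit order. Either fit it within each diagnosis group, which matches the 15 v 15 power statement, or pool the groups with diagnosis as a covariate; state which. Keep the planned diagnosis-by-intensity interaction. Do not extend the resting-value adjustment to the non-randomised ND-versus-AD contrast on this argument.

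Keep the unadjusted change-score test as a sensitivity analysis, and repeat the adjusted analysis in participants who rested first, where the resting scan cannot be affected by the exercise visit.

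In the sample size paragraph, replace the statement about reduced variation with the correlation it needs and the SD it is measured against. Give power over a range of r, ideally with SUVR-based SDs.

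The cost is SAP wording and one or two degrees of freedom (one more if diagnosis is added), plus up to about 4% more variance for r of about 0.3 to 0.5 on the quoted SDs. No new data are needed.

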### **B. Primary Outcome:**

We expect that the global FDG-PET signal will decline following a single bout of acute exercise in AD and ND subjects, and that the drop will be greater from rest to higher intensity exercise compared to the drop from rest to moderate intensity exercise. We further expect that individuals who have a greater lactate AUC in the exercise compared to resting condition (i.e. greater “lactate response”) will have greater drop in cerebral glucose metabolism. This likely means that they are exercising closer to their lactate threshold – the point where blood lactate concentrations begin to increase exponentially. Thus, we expect to see a negative linear relationship between change in lactate AUC and change in cerebral glucose metabolism, and a positive relationship between change in lactate AUC and change in cognitive performance.

### **C. Study results to participants:**

If participants request, we will provide them with their maximal VO2 value. Some participants find this data interesting. This value does not have any clinical or diagnostic implications so we do not expect any harm to come from providing this information.

#### **D. Publication Plan:**

Publication of the results of this study will be governed by the policies and procedures developed by the study team.

#### **APPENDIX I: VULNERABLE POPULATIONS**

Cognitively or decisionally impaired individuals: Any individuals with moderate or severe dementia be excluded from this study. Only individuals with very mild or mild dementia will be screened and scheduled. During Visit 1, the clinician will verify (based upon their full clinical examination) that participants can consent for themselves. If the clinician determines that the individual requires a surrogate decision maker, they will be excluded from the study. We will only enroll individuals deemed able to consent for themselves. In our experience, individuals with very mild or mild dementia (CDR 0.5 or 1) are able to consent for themselves while individuals with moderate or severe dementia (CDR 2 or 3 based on clinical examination) require surrogate consent.

